Recruitment: Participants will again be recruited through review of electronic medical records at Hennepin Healthcare. We will pull records of recent ACS hospital discharges, screening for depression where available. The ACE team may identify names from EPIC to facilitate this. We will also review records of outpatient cardiology (clinic and cardiac rehab to identify potential patients, (a flyer will be provided to patients and providers. Flyer attached). Opt out letters will be sent to all participants identified through chart review and HSR#17-4351 [05.17.17][10.05.17][07.26.18][09.09.19][10.22.19][11.04.19][01.28.20]

a research assistant will call patients on this list to screen for eligibility using the above criteria. Those that qualify by phone screen will be invited to an in person meeting to provide informed consent and then complete a baseline assessment. If study staff are unable to reach potentially qualifying patients by phone, study staff will work with care providers in clinic or cardiac rehab to introduce the study during a clinical visit, where research assistant will screen in person. The research assistant will then schedule the patient for a first session of BA-HD coaching at the Berman center, other Hennepin Healthcare facility, or in patient's home when needed; (Note that "Home" can be a nursing home, assisted living, rehab center, or other institution.). We may recontact patients who have completed primary outcome in other [name] Lab studies.

Behavioral Activation for Health and Depression (BA-HD)

Consistent with successful BA manuals, we plan to conduct up to 10 sessions of treatment over 12 weeks (the recommendation will be to do at least 8 sessions; scheduling of sessions will be flexible and conform to patient preference). The initial two sessions will be about 50 minutes long and later sessions will be 20-30 minutes long. Sessions can be done on site or over the phone. The recommended treatment will have 2 sessions in person followed by phone sessions. Home visits will be offered for sessions 1-2 if a participant cannot travel to on-site sessions. Study treatment will be conducted by an exercise physiologist who is a cardiac rehabilitation provider, a HHRI employed licensed social worker, or a licensed clinical health psychologist with clinical privileges at Hennepin Healthcare.

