Sessions 3-10 will be conducted by phone and will follow the same basic format: **1**) assess depressed mood, activity, and relevant behavioral risk factors between sessions, **2**) review adherence to activation goals from the previous session; **3**) choose 1-4 activation goals that are pleasant and/or in line with the participant’s values and explicitly schedule these; **4**) problem-solve barriers to completion of new goals, and **5**) offer an automated email or text message reminder of goals. Starting in session 4 the interventionist and participant will collaboratively discuss if the next relevant behavioral risk factor should be added to goals. During the final coaching call (session 10 if full protocol completed), rather than assigning new activation goals, the interventionist will guide the participant in completion of a written guide which provides a structure for continuing to work towards goals independently.

Measurement

Participants will complete self-report, interview, and anthropomorphic measures at enrollment and at end-of-treatment (i.e., following 12 weeks of BA-HD coaching). In addition, at end-of-treatment a 30-45 minute qualitative interview will be conducted. Participants will be compensated \$30 per assessment and an extra \$20 for completion of the qualitative interview. Thus, Aim II participants could receive \$80 total for assessments. Transportation will also be provided or reimbursed as well.

Variables assessed at baseline only: Socio-demographics, including age, gender, ethnicity, employment, and income will be collected. Medical history will be assessed through self-report and chart review and will include ACS diagnosis and treatment, and a detailed history of cardiac disease, events, and procedures. Co-Morbid conditions will also be assessed.

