Outcomes: Acceptability will be assessed only during the end-of-treatment assessment using the 8-item Client Satisfaction Questionnaire.⁹⁴ Feasibility will be assessed by rate of recruitment/retention, session attendance, and completion of between session goals. Depression symptoms will be assessed using the CESD and the 9-item self-report Patient Health Questionnaire (PHQ-9).⁹⁷ Composite Behavioral risk factor adherence: The Medical Outcomes Study Patient Adherence Questionnaire¹⁰⁶ has validated items measuring all four of the behavioral risk factors targeted (tobacco, physical activity, diet, medication adherence) and has been used in large studies of post-ACS risk factor change.¹¹³ Thus, we will use the total score of these items as a composite outcome across the 4 risk behaviors. We will calculate the total score for the 10 more general items related to cardiac health¹³⁵. We will also administer brief validated questions regarding time spent engaging in physical activity, medication adherence, and diet quality. Change in tobacco use will also be measured continuously with cigarettes/other tobacco product use per day and dichotomously using 7-day point prevalence abstinence (i.e., no use at all in past 7 days). A breath sample will be used to verify abstinence.^{117,118} Participants who report using smokeless tobacco products or e-cigarettes containing nicotine will be considered tobacco users. **Secondary outcomes:** We will also include established self-report measures of affect,¹¹⁹ health related quality of life¹²¹, exercise capacity,¹²² and hypothesized BA mediators.^{123,124} Weight/height, waist circumference, and resting systolic and diastolic blood pressure will be collected using standard procedures.

Analysis

Qualitative Data: We will again analyze recordings of end-of-treatment qualitative interviews using the Framework Matrix Analysis procedures described for Aim I above. However, analysis of follow-up interviews will explicitly focus on acceptability and suggestions for improving BA-HD.

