Feasibility and Acceptability Data will be examined descriptively. Client Satisfaction Questionnaire score, rates of recruitment/retention, session attendance, and completion of between session goals will be compared to relevant previous trials. **Clinical outcome analyses** will focus on determining if BA-HD had clinically meaningful effects. For example, we will examine within participant effect size and response rates (using standard cut offs) on the PHQ-9. We will examine within participant change in our composite of behavioral risk factors in a similar manner. We will analyze data in an intent-to-treat manner.

Design Considerations

Choice not to use cardiac rehabilitation. Cardiac rehabilitation is the gold standard for targeting behavioral risk factors post-ACS and also improves depression symptoms. However, only a minority of ACS patients complete cardiac rehabilitation and those with depression are particularly unlikely to attend or complete.¹²³ Thus, if we conducted our treatment in a rehabilitation setting we would miss many of those with depression post-ACS. **Choice to enroll participants 2-12 months after ACS.** We considered enrollment of patients while in the hospital for ACS. We chose not to because: 1) there is a high rate of spontaneous recovery of hospital assessed

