Minimization of loss of confidentiality/privacy: All data and records will be safeguarded according to the strict privacy/confidentiality policies of Hennepin Healthcare Research Institute's Institutional Review Board (IRB). Confidentiality will be maintained by numerically coding all data, disguising identifying information, and keeping data in secure electronic locations or locked in file drawers. All electronic data will be numerically coded and stored on a password protected computer in a secure research space. All paper forms will be stored in locked file cabinets in a locked room. Names of participants will be stored separately. Participant information will be accessible only to research staff, who are pledged to confidentiality and complete training in the ethical

conduct of research (i.e., both HIPAA and CITI trainings). [name] will also personally train staff on maintenance of participant confidentiality. Identifying information will not be reported in any publication.

Minimization of discomfort or distress when completing assessment and treatment procedures: We will take three specific steps to reduce the possibility of discomfort or distress:

Study will be clearly explained. A detailed explanation of the study, including what study participation would involve, the nature of the questions participants will be asked to answer, the nature of measurements, and the right to withdrawal from the study at any time without penalty, will be provided to the participants, both verbally and in writing (through the informed consent form). Participants will be encouraged to ask questions about the study. Individuals who are uncomfortable answering these types of questions, assessments, or interventions likely will not choose to participate. Those who choose to participate but are very uncomfortable with the questions, assessments or interventions will likely refuse these assessments or choose to withdrawal from the study.

Private setting. To help ensure clients' comfort, they will answer survey questions and complete physical measurements in a private setting. Thus, they should not be concerned that another individual would be able to observe these assessments.

Staff Training. All staff interacting with participants will be trained by [name] to ask questions and complete assessments in a sensitive manner and be supportive to any participant experiencing discomfort or distress.

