Analytic plan
Healthy Heart Habits (H³)

NCT04158219

R03HL136540

3/8/22

Analytic plan.

Means, standard deviations, frequencies, and percentages will be calculated to describe the sample. Because the intent of the open pilot trial was feasibility and acceptability assessment to inform additional treatment refinement, analysis will emphasize descriptive characterizations of the data and calculation of effect sizes to examine clinical magnitude of preliminary effects. Descriptive data on baseline characteristics and treatment engagement will be presented on the entire sample, regardless of trial completion. Treatment satisfaction and pre- to post- change were calculated only for completers. No correction for multiple comparisons will be made. Analyses were performed in Stata SE 16.

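### Does reporting satisfaction only for undefined completers make the acceptability result too favourable?

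*SAP*

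**What the plan says.** The SAP (Analytic plan) uses two analysis sets. For baseline and engagement it says: "Descriptive data on baseline characteristics and treatment engagement will be presented on the entire sample, regardless of trial completion". For the rest it says: "Treatment satisfaction and pre- to post- change were calculated only for completers". It does not say what makes someone a completer.

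The protocol (Measurement, Outcomes) fixes the timing of the satisfaction measure: "Acceptability will be assessed only during the end-of-treatment assessment using the 8-item Client Satisfaction Questionnaire". Who attends that assessment is set out just before: "Participants will complete self-report, interview, and anthropomorphic measures at enrollment and at end-of-treatment". The end-of-treatment point follows the 12 weeks of coaching, and no minimum number of sessions is attached.

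Two other places touch on finishing coaching. In the BA-HD section, up to 10 sessions are offered and "the recommendation will be to do at least 8 sessions". In the description of sessions 3 to 10, the last call is "session 10 if full protocol completed".

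Under Analysis, the protocol says that feasibility and acceptability data are examined descriptively and that the satisfaction score is compared with previous trials. It then turns to clinical outcomes and ends: "We will analyze data in an intent-to-treat manner".

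**The concern.** Acceptability is part of the stated aim, and the satisfaction questionnaire is its named quantitative measure. If people who dislike the programme leave, a score from those who remain flatters it. The protocol gives some ground for this: in Protections Against Risk it expects that participants who "are very uncomfortable with the questions, assessments or interventions will likely refuse these assessments or choose to withdrawal from the study". A flattering score would then be set beside scores from earlier trials and used in refining the treatment.

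The undefined term adds a second worry. If completer meant someone who finished coaching, at 8 or at 10 sessions, then a participant who stopped coaching but still came at week 12 would have a questionnaire on file that was not used. That loss would be avoidable, and it would sit badly with an intent-to-treat statement.

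**Working it through.** There is no planned figure to reproduce: the protocol gives N = 20 without an expected drop-out rate, a standard deviation or a target score. The check has two parts.

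**1. Which people does the term cover?**

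- The SAP sentence immediately before the restriction refers to trial completion, so the nearest meaning of completer is someone who completed the trial.
- The questionnaire exists only at end of treatment. A person not assessed then has no score, and no earlier value can stand in.
- The cell-phone amendment in the protocol refers to a 12-week outcomes visit, which supports reading end of treatment as a time point and not as a number of sessions.
- The 8 sessions are a recommendation within a flexible schedule. The mention of session 10 identifies which call is the last one. Neither is tied to an analysis set.

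On this reading, the completers with a satisfaction score are the people who answered the questionnaire. Rewriting the rule as everyone who answered selects essentially the same people.

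**2. How far could a score from stayers be off?**

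Input from the documents: N = 20. Assumed: L leavers, and a difference d between the means of stayers and leavers, in SD units. Then:

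- shift in the mean = (L/20) × d
- standard error of the stayers' mean = 1/√(20 − L)
- d at which the two are equal = standard error ÷ (L/20)

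| Leavers | Stayers | Standard error (SD) | Shift, d = 0 | Shift, d = 0.5 | Ratio to SE | Shift, d = 1 | Ratio to SE | d where shift = SE |
|---|---|---|---|---|---|---|---|---|
| 2 | 18 | 0.236 | 0 | 0.05 | 0.21 | 0.10 | 0.42 | 2.36 |
| 5 | 15 | 0.258 | 0 | 0.125 | 0.48 | 0.25 | 0.97 | 1.03 |
| 8 | 12 | 0.289 | 0 | 0.20 | 0.69 | 0.40 | 1.39 | 0.72 |

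The sign reverses if leavers would have scored higher.

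**The coaching reading, for comparison.** Assume 16 answer and 4 of them had stopped coaching. Leaving them out discards 4/16 = 25% of the forms. The standard error rises from 1/√16 = 0.25 to 1/√12 = 0.29 SD, and the mean moves by (4/16) × 0.5 = 0.125 SD at d = 0.5. This would be a real if modest loss, but nothing in the documents says the analysis is done this way.

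**The case for a change.** The strongest case for a change is that one sentence would remove the ambiguity at almost no cost, and that a shift below one standard error is still a bias. Extreme-case bounds make the point more sharply. If satisfaction were reduced to a yes/no rate and 14 of 16 were satisfied (87.5%), the rate among all 20 could lie anywhere from 14/20 = 70% to (14 + 4)/20 = 90%. With 11 of 12 (91.7%) it could lie from 11/20 = 55% to (11 + 8)/20 = 95%. Reporting engagement on everyone shows how many left, not what they thought, and the qualitative interview also takes place at end of treatment.

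All of that is correct, and the selection is real. But the width of those bounds comes from scores that do not exist, and it is the same whether the set is called completers or responders. The protocol also names a score, not a rate.

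Only collecting data from people who leave early would narrow the bounds. That would reverse the protocol's choice to assess acceptability at end of treatment only, and would mean contacting people who may have used their right to withdraw. It is probably too late in any case: the SAP is dated 3/8/22 and already speaks of these calculations in the past tense.

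The intent-to-treat argument is weaker for this outcome than it first appears. The sentence closes the text on clinical outcomes, while satisfaction is handled earlier as descriptive data. Even if it reached satisfaction, in a single-arm study it would supply no score for a person who never answered. Its tension with the completers-only rule for pre- to post-treatment change is more direct, but that is a separate matter.

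The evidence on direction is also thin. The expectation that uncomfortable participants will leave comes from text on distress during assessments and treatment procedures, and the protocol's section on potential risks says such discomfort was mild in earlier studies. People may also leave for unrelated reasons such as illness.

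**Conclusion.** No change to the plan follows. The term is undefined, but the surrounding text points to one sensible meaning, and on that meaning no collected questionnaire is dropped and no result would differ. An analyst would fill this gap without difficulty by summarising the scores that exist and stating how many there are. Retention is already a feasibility outcome and engagement is described for the whole sample, so a reader can see how many of the 20 the score leaves out. The feedback meant to refine the manual comes mainly from the qualitative interviews, which this SAP sentence does not restrict.

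What remains is the ordinary limit of a post-treatment satisfaction score: it describes those who stayed. Its direction and size cannot be determined from the documents. With 2 to 8 leavers scoring 0.5 SD lower, the overstatement is 0.05 to 0.20 SD, below the standard error in each case. It exceeds the standard error only under harsher assumptions, such as 8 leavers scoring 1 SD lower. This rests on the week-12 reading of completer and on assumed values for everything except N = 20. If the analysis had in fact dropped questionnaires from people who attended at week 12 after stopping coaching, the conclusion would differ, but neither document says so.
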